#### **EORTC QLQ-C30**

The EORTC QLQ-C30 consists of 30 questions that can be combined to produce 5 function scales (physical, role, cognitive, emotional, and social), 3 symptom scales (fatigue, pain, and nausea/vomiting), and a global measure of health status. The EORTC QLQ-C30 will be scored according to the EORTC QLQ-C30 scoring manual ([Fayers et al 2001](#)). An outcome variable consisting of a

score from 0 to 100 will be derived for each of the symptom scales, each of the function scales, and the global health status scale in the EORTC QLQ-C30 according to the EORTC QLQ-C30 scoring manual. Higher scores on the global health status and function scales indicate better health status/function, but higher scores on symptom scales represent greater symptom severity.

Definition of clinically meaningful changes

Changes in score compared with baseline will be evaluated. A minimum clinically meaningful change is defined as an absolute change of  $\geq 10$  in the score from baseline for scales from the EORTC QLQ-C30 (Osoba et al 1998). For example, a clinically meaningful improvement in physical function (as assessed by EORTC QLQ-C30) is defined as an increase of  $\geq 10$  in the score from baseline, whereas a clinically meaningful deterioration is defined as a decrease of  $\geq 10$  in the score from baseline. At each post-baseline assessment, the change in symptoms/ functioning from baseline will be categorized as improvement, no change, or deterioration as shown in Table 16. A patient’s best overall response in symptoms, function, or global health status/QoL will be derived as the best response the patient achieved, based on evaluable PRO data collected during the study period. Additional details will be provided in the SAP.

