#### Symptom improvement rate

The symptom improvement rate will be defined as the number (%) of patients with 2 consecutive assessments at least 14 days apart that show a clinically meaningful improvement (a decrease from baseline score  $\geq 10$  for EORTC QLQ-C30 symptom scales) in that symptom from baseline. The denominator will consist of a subset of the FAS who have a baseline symptom score  $\geq 10$ .

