#### 9.4.2.1 Primary endpoint: Progression-free survival

The primary analysis of the primary endpoint PFS will occur when it is expected that approximately 118 PFS events have occurred (79% maturity). PFS will be based on RECIST 1.1 using the Investigator tumor assessments. The analysis will be performed for patients in the FAS population using a stratified log-rank test adjusting for HRR status (mutant versus wildtype), PD-L1 tumor status (defined in Section 9.4.1.4) and Bajorin risk index (0 [defined as no risk factors for metastasis and ECOG performance status] versus 1 [defined as 1 risk factor] versus 2 [defined as 2 risk factors]). The effect of durvalumab + olaparib versus durvalumab + placebo will be estimated by the HR together with its 95% CI from a stratified Cox model (an HR less than 1 will favor durvalumab in combination with olaparib).

KM plots of PFS will be presented by treatment arm, by treatment arm and HRR status (mutant versus wildtype), by treatment arm and PD-L1 tumor status, and by treatment arm and Bajorin risk index where appropriate. Summaries of the number and percentage of patients experiencing a PFS event and type of event (RECIST 1.1 or death) will be provided along with the median PFS for each treatment.

The assumption of proportionality will be assessed.

Sensitivity analyses will be performed to assess possible evaluation-time bias that may be introduced if scans are not performed at the protocol-scheduled timepoints. The midpoint between the time of progression and the previous evaluable RECIST 1.1 assessment will be analyzed using a stratified log-rank test as described for the primary analysis of PFS. For patients whose death was treated as a PFS event, the date of death will be used to derive the PFS time used in the analysis. This approach has been shown to be robust even in highly asymmetric assessment schedules ([Sun and Chen 2010](#)).

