#### **9.4.2.4 Objective response rate**

The ORR will be based on RECIST 1.1 using the Investigator tumor data. The ORR will be compared between durvalumab + olaparib and durvalumab + placebo using logistic regression models adjusting for the same factors as the primary and secondary endpoint PFS dependent on the population being analyzed. The results of the analysis will be presented in terms of an odds ratio together with its associated profile likelihood CI and p-value (based on twice the change in log-likelihood resulting from the addition of a treatment factor to the model).

Summaries will be produced that present the number and percentage of patients with a tumor response (CR/PR). Overall visit response data will be listed for all patients (ie, the FAS). For each treatment arm, best overall response (BoR) will be summarized by n (%) for each category (CR, PR, SD, PD, and NE). No formal statistical analyses are planned for BoR.

The ORR analysis described above will be repeated for a subset of patients in the FAS with HRRm.

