#### **EORTC QLQ-C30**

Time to symptom deterioration in symptom, function, and HRQoL will be analyzed respectively for each of the 3 multiple-item symptom scales (fatigue, pain, and nausea/vomiting), the 5 function scales (physical, role, cognitive, emotional, and social), and global health status/QoL. These analyses will be performed for the FAS using a log-rank test stratified by the same covariates as for the primary PFS endpoint and illustrated using a KM plot by treatment arm. Summaries of the number and percentage of patients who have an event, as well as who were censored, will be provided along with the medians for each treatment.

A summary of the symptom improvement rate for each of the 3 symptom scales will be produced. Similarly, a summary of the best HRQoL/function response rate for each of the 5 function scales and global health status/QoL will be produced. The best symptom response rate and HRQoL/function response rate will be analyzed by comparing the treatment arms using a logistic regression model as described for the analysis of ORR. The odds ratio, p-value, and 95% CI will be presented graphically on a forest plot.

Summaries of absolute and change from baseline values for each of the 3 symptom scales/items, 5 individual symptom items (dyspnea, loss of appetite, insomnia, constipation, and diarrhea), 5 function scales and the global health status/QoL score, and each functional domain will be reported by visit for each treatment arm. The mean change from baseline will be analyzed for each symptom scale and function scale of interest using a mixed model for repeated measures and potentially a piecewise linear model to further support data interpretation. Full details of this and appropriate sensitivity analyses will be described in full in the SAP.

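### The PRO improvement-rate logistic models leave out the scale's own baseline score; adding it costs almost nothing and removes a dependence on chance baseline imbalance

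*Protocol*

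**What the plan says.** Section 9.4.2.7 (EORTC QLQ-C30) compares the symptom and HRQoL/function response rates between arms with a model specified by cross-reference. The rates "will be analyzed by comparing the treatment arms using a logistic regression model as described for the analysis of ORR". Section 9.4.2.4 describes that model as "using logistic regression models adjusting for the same factors as the primary and secondary endpoint PFS dependent on the population being analyzed". Section 9.4.2.1 names the PFS factors in the "stratified log-rank test adjusting for HRR status (mutant versus wildtype), PD-L1 tumor status (defined in Section 9.4.1.4) and Bajorin risk index", and Table 17 lists the same three.

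Time to deterioration is tested in Section 9.4.2.7 "using a log-rank test stratified by the same covariates as for the primary PFS endpoint". Table 17 plans a log-rank test for it and no Cox model.

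Baseline enters in two other ways. First, it defines the event: improvement requires "2 consecutive assessments at least 14 days apart that show a clinically meaningful improvement", meaning at least 10 points from baseline. Second, it limits the analysis subset. For symptom improvement, "The denominator will consist of a subset of the FAS who have a baseline symptom score" of at least 10, and Section 9.4.1.3 sets matching cut-offs (at least 10 or at most 90) for the other PRO endpoints. The baseline score itself is not a covariate in either the logistic models or the log-rank tests.

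**The concern.** A 10-point change from baseline depends on where the patient starts. Someone who enters with an unusually bad score has more room to improve and tends to drift back towards the average without any treatment effect. Someone who enters well tends to drift the other way. If one arm happens to start worse on a scale, it will show more improvers and fewer deteriorations on that scale for that reason alone.

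HRR status, PD-L1 status and Bajorin index were chosen for tumour endpoints. Bajorin carries ECOG 0 or 1 versus 2 (Section 6.4.1), so it takes up some of the baseline difference in physical function, but it is not the score from which change is measured.

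Global health status/QoL, physical function, fatigue and pain are named secondary endpoints (Section 3, Table 3), and the response-rate comparison is reported with an odds ratio, p-value and 95% CI. At stake is how far those figures, in the single randomization observed, reflect treatment and how far they reflect the starting scores.

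**Working it through.** **Inputs from the protocol.** 150 patients, 1:1, so 75 per arm (Section 9.2); two-sided tests with 95% CI (Section 9.4); event and subset definitions from Section 9.4.1.3. The protocol states no SD, effect size or power for any PRO endpoint, so there is no PRO figure to reproduce. As a check of the tools only, the stated PFS power does reproduce: √118/2 × |ln 0.55| − 1.96 = 1.287, which gives 90.1% against the stated 90%.

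**Assumptions (not in the protocol).** Baseline SD 20 to 30; baseline-to-follow-up correlation 0.3 to 0.7; true effect 8 or 10 points where power is shown.

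**Step 1: size of chance imbalance.** The SE of the baseline mean difference is SD × √(2/75).
- SD 20: 3.3 points; a gap above 5 points in about 13% of trials.
- SD 25: 4.1 points; about 22%.
- SD 30: 4.9 points; about 31%.

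These are per scale, for full arms on an unbounded scale.

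**Step 2: improvement-rate logistic model.** 2000 simulated trials per scenario, 75 per arm, symptom scale with mean 50 bounded at 0 and 100, baseline at least 10, improvement of at least 10 at two consecutive visits. Each trial was analysed without and with the baseline score. The three stratification factors were not simulated. The slope is the change in estimated log odds ratio per point of baseline gap with no treatment effect. Each pair is without → with baseline.

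| SD, correlation | Type I error, all trials (%) | Share with gap >5 (%) | Type I error given gap >5 (%) | Slope per point | Power, 10-point effect (%) |
|---|---|---|---|---|---|
| 25, 0.5 | 5.2 → 5.4 | 16.9 | 11.0 → 6.8 | 0.043 → 0.004 | 49.5 → 55.1 |
| 20, 0.5 | 5.6 → 5.4 | 11.1 | 12.7 → 6.3 | 0.055 → 0.005 | 66.9 → 74.2 |
| 25, 0.7 | 4.4 → 4.7 | 16.4 | 5.2 → 4.0 | 0.034 → 0.004 | 70.3 → 72.5 |
| 25, 0.3 | 3.9 → 4.4 | 17.1 | 8.5 → 4.1 | 0.046 → -0.003 | 39.4 → 46.5 |

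A 5-point gap therefore multiplies the odds ratio by exp(5 × 0.034) = 1.19 to exp(5 × 0.055) = 1.32. The conditional error rates are imprecise: 11.05% of 2000 is 221 trials, so the 12.7% has a simulation SE of √(0.127 × 0.873/221) = 2.2 points.

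**Step 3: a second model of the data.** 75 per arm, up to five visits with dropout, scores in realistic steps, 8-point effect. Power went from 46.1 to 48.5% (QoL-like scale), 46.0 to 48.0% (fatigue-like) and 40.0 to 39.4% (pain-like) when baseline was added. On the fatigue-like scale the control improvement rate rose from 28% at a baseline of 11 to about 55% at 89, which shows the dependence directly.

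**Step 4: time to deterioration.** 2000 trials per scenario, eight visits, baseline at most 90, no treatment effect, unstratified log-rank test. Overall type I error was 4.7 to 5.6%. In trials with a gap above 5 points it was 8.1 to 10.8%. The correlation between baseline gap and test statistic was -0.34 to -0.46. An adjusted Cox model was not simulated, so its gain is not quantified here.

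**The case against.** The planned tests are valid. Averaged over randomizations, type I error is nominal for both methods, and any randomized comparison that omits a prognostic covariate varies with chance imbalance. That stands: this is an improvement in precision and interpretability and does not correct an invalid analysis.

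The average gain is small, and one scenario shows a slight loss. That also stands. A reader might infer a much larger cost from a contrast in the second simulation: power is about 60% when the baseline gap lies more than one SD of its chance distribution in one direction, and 31 to 36% when it lies that far in the other. Those are opposite tails of imbalance, so the contrast is not what the trial loses on average.

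Some of the problem is already handled. Bajorin includes ECOG, and the cut-offs in Section 9.4.1.3 remove patients who cannot move 10 points. Both count in part. Because the simulations in Steps 2 and 4 omitted the stratification factors, their conditional figures are somewhat too large, by an amount that cannot be derived from the documents. The cut-offs do nothing for the patients who remain.

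Covariates can be settled in the SAP, and Section 9.4 calls itself a summary. An SAP could add the baseline score. But the protocol does fix a factor list for these models by cross-reference. The SAP deferral in Section 9.4.2.7 follows the mean-change sentence, and the note under Table 17 speaks of combining or removing factors and not of adding one. For the same reason a reader should not extend this point to the mixed model for mean change, whose details are left to the SAP.

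**Conclusion.** The point holds as a minor improvement at almost no cost. As written, the improvement/response-rate models omit the one covariate from which the endpoint is computed. The consequence is an odds ratio that shifts with chance baseline imbalance: about 1.2 to 1.3-fold for a 5-point gap, when the SE of that gap is 3 to 5 points. Power usually falls a little short of what the same data could give (-1 to +7 percentage points from adding baseline). All these sizes rest on assumed SDs, correlations and effects.

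A reader might infer that the PRO p-values are invalid or that a confirmatory claim is at risk. The documents do not support this. Simulated type I error is about 4 to 6% overall. Section 9.1 defines success on PFS alone, and Sections 9.1 and 9.4.10 pass alpha from PFS to OS only, so the PRO endpoints carry none.

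**What to change.** In Section 9.4.2.7, state that each improvement/response-rate logistic model includes the continuous baseline score of the respective scale in addition to HRR status, PD-L1 status and Bajorin index.

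For time to deterioration, keep the stratified log-rank test as the formal test. Add, labelled as supportive, a hazard ratio from a newly specified Cox model stratified by the same factors with baseline score as a covariate. Saying which result governs avoids two competing answers.

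Cost: a sentence or two and no new data, since the QLQ-C30 is already scheduled at Cycle 1 (Table 1). No patient is lost from the logistic models, because the subset cut-offs already require a baseline score. The odds ratio and hazard ratio become conditional on baseline and should be described that way. The change should be made before unblinding, since adding a covariate afterwards would look driven by the data.

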#### **EQ-5D-5L**

Descriptive statistics, graphs, and listings will be reported for health state utility index values (United Kingdom base case) and visual analog scale by visits as well as change in these scores from baseline. To support future economic evaluations of the study treatment, additional appropriate analyses may be undertaken, for example, mean health state utility pre- and post-dose and pre- and post-progression.

## **PGIC**

Responses on the PGIC will be summarized descriptively as the number of patients and corresponding percentages for each category in the questionnaire at each visit by treatment arm.

### **9.4.3 Safety analyses**

Safety and tolerability data will be presented by treatment arm using the safety population.

Data from all cycles of treatment will be combined in the presentation of safety data. AEs (both in terms of MedDRA preferred terms and CTCAE grade) will be listed individually by patient. The number and percentage of patients experiencing each AE will be summarized by treatment arm and CTCAE grade. Additionally, data presentations of the rate of AEs per person-years at risk may be produced. Any safety summaries examining retreatment with durvalumab will be produced separately as described in the SAP.

Other safety data will be assessed in terms of physical examination, serum chemistry, hematology, vital signs, and ECGs. Exposure to study treatment, time on study, dose delays, and dose reductions will also be summarized. At the end of the study, appropriate summaries of all safety data will be produced, as defined in the SAP.

### **9.4.4 Pharmacokinetic analyses**

PK concentration data will be listed for each patient and each dosing day, and a summary will be provided for all evaluable patients.

### **9.4.5 Immunogenicity analyses**

Immunogenicity results will be analyzed descriptively by summarizing the number and percentage of patients who develop detectable ADAs against durvalumab. The immunogenicity titer and presence of neutralizing ADA will be reported for samples confirmed positive for the presence of ADAs. The effect of immunogenicity on PK, pharmacodynamics, efficacy, and safety will be evaluated, if data allow.

### **9.4.6 Pharmacokinetic/pharmacodynamic relationships**

If the data are suitable, the relationship between PK exposure and efficacy/safety parameters may be investigated graphically or using an appropriate data modeling approach.

#### **9.4.7 Biomarker data**

The relationship of PD-L1 expression and, if applicable, exploratory biomarkers to clinical outcomes (including but not restricted to PFS) may be assessed.

PD-L1 expression determined by IHC will be reported in the CSR. Summaries and analyses for exploratory biomarkers will be documented in a separate analysis plan and will be reported outside the CSR in a separate report.

#### **9.4.8 Pharmacogenetic data**

DNA variants associated with response, including AEs and/or cancer or its evolution, are exploratory. These exploratory analyses are not expected to be reported in the CSR, but any contribution to the interpretation of the results may be included and will be clearly labeled as exploratory.

#### **9.4.9 Exploratory analyses**

Associations between exploratory endpoints and OS, PFS, ORR, and DoR may be assessed. These exploratory endpoints may include, but are not limited to, HRR gene expression assessments, protein expression detected by IHC (eg, PD-L1), ctDNA, tumoral mutations beyond HRRm, and mRNA expression.

The biomarker analyses to be investigated using tumor samples may include, but not limited to, the following:

- Study the correlation of the HRRm signature with response. Retrospectively adapt/refine olaparib HRRm signature based on emerging data from clinical studies particularly in bladder cancer.
- Explore the impact of PD-L1 expression and tumor mutations on response to treatments and correlations between HRRm, mutations in other genes and PD-L1 expression.
- Explore the correlation between TMB and microsatellite instability with genetic alterations and clinical response.
- Explore association of immune-related gene expression signatures such as, but not limited to, IFN $\gamma$  gene expression signature in tissue with response to treatment.
- Based on emerging scientific knowledge, further analyses yet to be defined may be undertaken.

Analyses of ctDNA include, but may not be limited to, the following:

- Exploring association of genetic variants and/or variant burden in genes in ctDNA with response to treatment and other exploratory biomarkers.
- Comparing genetic variants in FFPE to those in ctDNA, particularly, but not limited to, HRRm, and their correlative response to treatment.
- Exploring changes in ctDNA mutation frequencies, including, but not limited to, changes in mutant allele frequency over the course of treatment as an early indicator of clinical outcome.

Exploratory analyses are not expected to be reported in the CSR but any contributing to interpretation of the results may be included and will be clearly labeled as exploratory.

#### **9.4.10 Methods for multiplicity control**

Formal adjustment of alpha for multiple comparisons is not planned, but if required at the time of reporting, 100% of the alpha used for the primary PFS analysis will be used for the OS analysis if the PFS analysis is statistically significant.

For the OS endpoint, there is 1 interim analysis planned, and the alpha level will be controlled at the interim and primary analysis timepoints by using the Lan-DeMets ([Lan and DeMets 1983](#)) spending function that approximates an O'Brien Fleming approach.

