## 9.1 Statistical hypotheses

The primary objective is to assess the efficacy of durvalumab + olaparib combination therapy compared with durvalumab + placebo in terms of PFS for patients in the full analysis set (FAS). The secondary objective is to assess OS in the FAS. Thus, formal statistical analyses will be performed to test the main hypotheses:

- Null Hypothesis 1 ( $H_{10}$ ): No difference between durvalumab + olaparib compared with durvalumab + placebo in terms of PFS
- Alternative Hypothesis 1 ( $H_{11}$ ): There is a difference between durvalumab + olaparib compared with durvalumab + placebo in terms of PFS

If a statistically significant difference is observed in the study, ie, reject the null hypothesis of no difference in favor of  $H_{11}$ , then the following hypotheses can also be tested:

- Null Hypothesis ( $H_{20}$ ): No difference between durvalumab + olaparib compared with durvalumab + placebo in terms of OS
- Alternative Hypothesis ( $H_{21}$ ): There is a difference between durvalumab + olaparib compared with durvalumab + placebo in terms of OS

To control for type 1 error, a significance level of 5% will be used for the analysis of PFS. If the null hypothesis ( $H_{10}$ ) of no effect is rejected, 100% of the alpha can be passed to the OS secondary endpoint to test  $H_{20}$ .

The study will be considered positive (ie, a success) if durvalumab + olaparib combination therapy is statistically different from durvalumab + placebo in terms of PFS.

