## 9.2 Sample size determination

The study is sized to characterize the PFS benefit of durvalumab in combination with olaparib versus durvalumab monotherapy in first-line patients with unresectable Stage IV UC.

Approximately 150 patients globally will be randomized in a 1:1 ratio to either the durvalumab + olaparib treatment group or the durvalumab + placebo treatment group, 75 patients per arm. The randomization will be stratified based on HRR status (mutant versus wild type) and Bajorin risk index (0 versus 1 versus 2).

The DCO for the primary analysis of PFS will occur when approximately 118 PFS events have occurred across both treatment groups (79% maturity). Assuming a median survival of 3 months for durvalumab monotherapy and recruitment of 150 patients in 6 months, it is estimated that this DCO will occur 7 months following recruitment of the last patient.

If the true PFS hazard ratio (HR) is 0.55 (likely to correspond to an 82% prolongation of PFS), the study will have 90% power to demonstrate a statistically significant difference for PFS at the 2-sided 5% significance level.

The smallest treatment difference that could be statistically significant at the primary analysis of PFS is an HR of 0.69 (assuming a 2-sided p-value of 0.5).

There will be up to 2 analysis timepoints for OS. The first OS analysis will occur at the same time as the primary PFS analysis and will be based on an estimated 44 OS events across therapies (29% maturity), and the second OS analysis will occur when

approximately 100 OS events have occurred (67% maturity). With an approximate 6-month recruitment period and an assumed median OS of 16 months in the durvalumab + placebo arm, it is anticipated that the final analysis will be performed at approximately 27 months after the last patient has been recruited.

Assuming the true OS HR is 0.75, the study will have 30% power to demonstrate a statistically significant OS effect with a 5% 2-sided significance level, allowing for 2 analyses of the data. The smallest treatment difference at the second analysis of OS that could be statistically significant is an HR of 0.68.

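### Section 9.1 tests OS only after PFS is rejected, but Section 9.4.10 makes that sequence optional at a time when PFS is already unblinded.

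*Protocol*

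**What the plan says.** Section 9.1 sets out a two-step sequence with a stated purpose: "To control for type 1 error, a significance level of 5% will be used for the analysis of PFS". If the PFS null is rejected, "100% of the alpha can be passed to the OS secondary endpoint to test" the OS null. The OS hypotheses are introduced as testable once a significant PFS difference has been seen, and nothing there makes the sequence depend on a later request.

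Section 9.4.10, on multiplicity control, opens differently: "Formal adjustment of alpha for multiple comparisons is not planned, but if required at the time of reporting, 100% of the alpha used" for PFS will be used for OS if PFS is significant. Its next paragraph fixes Lan-DeMets spending of the O'Brien-Fleming type across the interim and final OS analyses, without any condition. Section 9.5 repeats that spending rule. It also says that the study is unblinded for the single PFS analysis at about 118 events, with the OS interim at the same point.

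The success rule in Section 9.1 rests on PFS alone: "The study will be considered positive (ie, a success) if durvalumab + olaparib combination therapy is statistically different from durvalumab + placebo" in terms of PFS.

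**The concern.** Both sections describe the same transfer of alpha from PFS to OS. In 9.1 the transfer is the method of error control. In 9.4.10 it applies only if someone asks for it when results are reported. The two give different answers in one case: PFS is not significant and OS looks favourable. Under 9.1 no formal OS claim is available. Under 9.4.10 a reader could argue that no adjustment was planned and that the OS p-value may be judged on its own.

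The case is foreseeable. Section 4.2.1 itself remarks that OS has been the more robust measure of benefit with immuno-oncology monotherapy, although it argues that PFS suits the addition of olaparib. OS is the key secondary endpoint, with its own power statement, critical hazard ratios and alpha levels, so it is not purely descriptive.

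Timing makes this matter. By the estimates in Section 9.2, the PFS cutoff falls about 7 months, and final OS about 27 months, after the last patient is recruited. Any decision at reporting is taken with PFS known, and for final OS with the interim OS result known too. A multiplicity rule chosen at that stage does not control error.

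**Working it through.** **Inputs.** From Sections 9.1, 9.2 and 9.5: PFS at 2-sided 5%; 118 PFS events; PFS HR 0.55; 1:1 allocation; OS at an overall 2-sided 5% over two looks (about 44 and 100 events); OS HR 0.75; final OS level 4.85%. The protocol gives no correlation between the PFS and OS statistics, so the values below are assumptions.

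**Step 1: the plan's own figures.** Section 9.2 states that "the study will have 90% power to demonstrate a statistically significant difference for PFS at the 2-sided 5% significance level". With the Schoenfeld formula for 1:1 allocation, power = Φ(√d/2 × |ln HR| − z):

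- PFS: √118/2 × |ln 0.55| − 1.960 = 5.431 × 0.598 − 1.960 = 1.287, so power is 90.1%. The stated 90% reproduces, as do the 118 events.
- OS: √100/2 × |ln 0.75| − 1.973 = 5 × 0.288 − 1.973 = −0.535, so power is 29.6% against the stated 30%.

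The conflict over the gate therefore touches no sample size, event count or power figure.

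**Step 2: error with the 9.1 gate.** If both nulls are true, a false claim requires a PFS rejection first, so its chance is at most 5%. If only the OS null is true, a false claim requires an OS rejection, again at most 5%. If only the PFS null is true, the PFS test itself holds 5%. Familywise error is at most 5% in every case.

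**Step 3: error without the gate.** Suppose OS is tested at 2-sided 5% whatever PFS shows, and both nulls are true. Then the error is P(|Z₁| > 1.96 or |Z₂| > 1.96), with Z₁ and Z₂ bivariate normal with correlation ρ. At ρ = 0 it is 1 − 0.95² = 9.75%.

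| ρ (assumed) | Familywise error |
|---|---|
| 0 | 9.75% |
| 0.3 | 9.51% |
| 0.5 | 9.07% |
| 0.7 | 8.35% |
| Bonferroni bound | 5% + 5% = 10% |

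The figures for ρ above 0 treat OS as one test at 5% and not as two looks. The independence figure and the bound need only the overall 5% for OS.

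**Step 4: direction.** Under the PFS null, the 5% chance of a significant difference splits into 2.5% favouring the combination and 2.5% against it. Requiring HR <1 in the success rule makes the chance of a false declaration of success 2.5% instead of 5%.

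**The case against.** The other side has four points of weight.

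First, the two sections can be read together. A fixed sequence needs no splitting of alpha, so one may say that no formal adjustment is planned and still intend the sequence. Section 9.1 is also permissive: it says what can be tested, not what must be. Neither section states that OS may be tested at 5% after a non-significant PFS. This narrows the conflict but does not remove it, because 9.4.10 still makes the sequence itself conditional on a requirement arising at reporting.

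Second, Section 9 requires the SAP to be signed off before any potentially treatment-revealing data are reviewed, and Section 9.4 requires it before database lock. The SAP may settle the point. But Section 9 also allows final amendments up to reporting, so the protocol does not close the gap.

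Third, the error rates in the working belong to a procedure that the protocol does not prescribe. A reader might infer that the plan has a 9.75% error rate, or that no alpha control is planned at all. The documents support neither. The first needs the gate to be dropped and PFS and OS to be independent, although a death without prior progression counts in both endpoints. The second overlooks the unconditional spending rule across the OS looks.

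Fourth, a reader might infer from the wording of the success rule that a significantly worse PFS would be declared a success and would release alpha to OS. Read as a whole, the protocol does not support that. The Synopsis and Section 9.4.2.1 say that an HR below 1 favours the combination, Section 4.2.1 says that the design aims at improvement in PFS, and Section 9.2 sizes the study on PFS benefit and gives critical hazard ratios only below 1. A non-directional alternative with a 2-sided test is ordinary. What remains is a small gap in wording.

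**Conclusion.** The concern holds in a limited form. Sections 9.1 and 9.4.10 conflict on whether the PFS-to-OS sequence is a fixed part of the plan, and 9.4.10 defers the answer until PFS is unblinded. If the gate were then not applied and OS were tested at 2-sided 5%, familywise error under the global null would be about 8.3% to 9.75% instead of 5%, for assumed correlations from 0.7 down to 0, and could not exceed 10%.

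The effect is confined to the validity of an OS claim after a non-significant PFS. An isolated OS result cannot make the study positive, because success rests on PFS alone, so the false-positive rate for study success stays at 5%. In a Phase II trial with 30% stated power for OS, this is a point that should be fixed, not one on which the trial's main conclusion depends. The missing direction in the success rule is editorial.

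**What to change.** In Section 9.4.10, delete the words saying that adjustment is not planned and is made only if required at reporting. State instead, without condition, that OS is formally tested, at the Lan-DeMets levels already specified, only if PFS is significant at 2-sided 5%, and that otherwise OS is reported with nominal p-values and no formal claim.

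As a minor edit in Section 9.1, add to both the success rule and the condition for testing OS that the PFS difference must favour durvalumab + olaparib (HR <1). This matches the direction already implied in the Synopsis and Sections 4.2.1, 9.2 and 9.4.2.1.

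The cost is a few sentences. The 150 patients, 118 PFS events, 100 OS events and stated powers stay as they are. The sponsor gives up only the option to choose the rule after seeing PFS. The change has its full value only if made before PFS is unblinded.
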